### Population

#### Inclusion criteria

1.  $\geq 18$  years old.
2. Admitted to the ICU of a participating study site.
3. At least one measurement of energy expenditure performed during ICU stay.

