## Intervention/exposure

Study subjects will be followed until ICU discharge or death, whichever occurs first.

All participating centers are encouraged to modify local nutrition protocols to recommend that:

- Indirect calorimetry is performed under standardized conditions (Appendix 1).
- Indirect calorimetry is performed within 3 days of ICU admission.
- Indirect calorimetry is repeated every 3-4 days until ICU discharge, death or in the event of limitations in treatment to best supportive care.
- Oxygen consumption ( $VO_2$ ), carbon dioxide production ( $VCO_2$ ), RQ and resting energy expenditure (REE) are documented in the patient's medical records.

Interpretation of investigations and energy prescriptions are left to the discretion of the attending physician or dietitian and are not regulated by the study protocol in any way.

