## Data collection

Pseudonymized patient data is reported from participating study sites through a secure online platform (Redcap™) on 1) admission, 2) on the day of each indirect calorimetry, and 3) on ICU discharge or death.

Participating centers are responsible for creating and maintaining a secure code key linking the study number attributed to a patient with a patient ID, to be stored in a secure location at the study site.

On admission:

- Admission date
- Admission diagnosis (ICD-10)
- Surgery prior to admission (YES/NO), elective or emergent
- ICU source of admission (Emergency department, ward, operating theatre, other ICU).
  - If ward or operating theatre → days in hospital before ICU admission.
  - If other ICU → days in previous ICU before admission.
- Outcome prediction score (SAPS 3, APACHE III/IV, MPM, etc.) and risk of death on admission (%)
- Demographic and anthropometric data:
  - Sex (male/female)
  - Age (years)
  - Actual body weight (kg)
  - Height (cm)
- Chronic comorbidities registered in electronic health records (YES/NO):
  - Hypertension
  - Ischemic heart disease
  - Heart failure

- Diabetes mellitus
- COPD
- Chronic kidney disease
- End-stage renal disease
- Liver cirrhosis
- Active cancer (not in complete remission)
- Haematological malignancy
- Solid organ transplant

On the day of each indirect calorimetry:

- REE (kcal/24 h), RQ,  $\text{VO}_2$  (ml/min),  $\text{VCO}_2$  (ml/min) and date of investigation
- Invasive mechanical ventilation (YES/NO) or renal replacement therapy (YES/NO)
- If YES to invasive mechanical ventilation:
  - fraction of inspired oxygen
  - positive end-expiratory pressure (cm  $\text{H}_2\text{O}$ )
- Sequential organ failure assessment (SOFA) score
- Fever ( $\geq 38.5^\circ\text{C}$ ) within 2 hours of measurement (YES/NO/MISSING)
- Results of daily blood tests if available from routine testing:
  - P-CRP (mg/L)
  - P-albumin (g/L)
  - P-urea (mmol/L)
  - P-creatinine ( $\mu\text{mol/L}$ )
  - Haemoglobin (g/L)
- Infusions of vasoactive medications (YES/NO, if YES → name of medication(s))
- Infusions of sedatives or analgesics (YES/NO, if YES → name of medication(s), if propofol → infusion rate at time of measurement)
- Infusions of parenteral and/or enteral nutrition (YES/NO, if YES → formulation and rate at time of measurement)
- Richmond Agitation-Sedation Scale (RASS) score on day of measurement

On discharge:

- Discharge date
- Survival status (ALIVE/DEAD)

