## Sample size considerations

The goal of this study is to include  $\geq 200$  patients with an ICU length of stay of  $>10$  days. Based on data from the Swedish Intensive Care Registry between 2015-2019, these patients accounted for 5% of all ICU admissions [9]. This proportion is comparable to results from a registry study conducted in Australia and New Zealand of over one million ICU admissions [8]. Based on these figures we intend to screen 6000 unique patients for study participation, accounting for the possibility that multiple measurements of indirect calorimetry are not consistently performed. Based on Swedish registry data approximately 1250 unique patients with at least one measurement of indirect calorimetry will be included in the analysis.

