Frequencies and patterns of missing data will be investigated for each outcome and explanatory variable by studying summary tables and plots. If missing at random can be assumed and frequencies are below 3% at each time point, this missingness will be ignored, and observations dropped. Explanatory variables with more than 30% missing values at baseline will not be considered, except for the SOFA score, which is not available in the Australian subpopulation. SOFA score will be investigated in non-Australian patients only. As an exploratory analysis, the SOFA score will be imputed in the Australian cohort. Multiple imputation will also be investigated for explanatory variables between 3 and 30% missing values at baseline. If missing at random cannot be assumed, alternative modelling approaches will be considered. Conditional logistic regression will be used to calculate the inverse probability of censoring weights to control for selective drop-out in patients discharged alive from the ICU.

For hypothesis-generating purposes, longitudinal K-means clustering or clustering with dynamic time warping will be used to investigate potential subpopulation phenotypes based on transitions in energy expenditure over time, as appropriate.

All analyses will be performed in R version 4.4.0 or later. The predetermined level of statistical significance for the primary outcome is set to  $\leq 0.05$ . For all other outcomes, no adjustments for multiple comparisons will be made due to the explorative nature of this part of the study. Hypotheses will be generated for target populations with similar characteristics as our sample population, leaving external validity investigations to future confirmatory studies.

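### A skipped calorimetry leaves no record and the SAP defines no expected measurements, so state-driven gaps in REE and RQ while patients are still in ICU may go unseen and have no named method

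*Combined protocol and SAP*

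**What the plan says.** - **Schedule.** The protocol (Intervention/exposure) makes it a recommendation: "All participating centers are encouraged to modify local nutrition protocols to recommend that" a first calorimetry is done within 3 days, and then "Indirect calorimetry is repeated every 3-4 days until ICU discharge, death or in the event of limitations in treatment to best supportive care". Entry needs only this: "At least one measurement of energy expenditure performed during ICU stay".
- **Skipping is foreseen.** Sample size considerations sets the screening number "accounting for the possibility that multiple measurements of indirect calorimetry are not consistently performed".
- **Records.** Under Data collection, patient data are reported "on 1) admission, 2) on the day of each indirect calorimetry, and 3) on ICU discharge or death". SOFA, FiO2, PEEP, CRP and the other time-varying items belong to the calorimetry-day form. Admission, investigation and discharge dates are collected. No listed item captures a calorimetry that was due but not done, or the date of limitation to best supportive care.
- **Missing data.** The SAP states: "Frequencies and patterns of missing data will be investigated for each outcome and explanatory variable by studying summary tables and plots". Missingness below 3% at each time point may be ignored if missing at random (MAR) can be assumed. Multiple imputation is named for explanatory variables only. If MAR cannot be assumed, other modelling is to be considered, without detail. Conditional logistic regression will supply "inverse probability of censoring weights to control for selective drop-out in patients discharged alive from the ICU".
- **Model.** The SAP uses a generalised linear mixed model with random intercepts for patient and site. Its time variable is the ICU day of the measurement.
- **Feasibility.** Appendix 1 advises against measuring when there are significant leaks, and refers users to the manual at FiO2 above 0.70 or PEEP above 10. It makes documentation of VO2 and VCO2 optional.

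**The concern.** A missing-data check needs a denominator. For REE and RQ the natural one is the number of calorimetries due while the patient was in ICU, and the SAP does not define it. If rows in the database serve as the denominator, a row exists only because a calorimetry was done, so REE and RQ will be nearly complete by construction and the 3% rule will be met whatever was skipped.

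The primary outcome is change in REE over time in patients staying more than 10 days, so it depends on who is still being measured late in the stay. If that depends on the patient's condition on the day, the late mean describes a selected subset. The analysts could then report a complete outcome and never reach the SAP's provision for data not missing at random. The weights would not help, because they address leaving the ICU alive and not going unmeasured while still there.

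**Working it through.** **1. The plan's own figures.** Sample size considerations gives 6000 screened and 5% staying more than 10 days: 6000 x 0.05 = 300, against a goal of 200. The margin is (300 - 200)/300 = 33%. No loss rate is stated. The margin is in patients, not measurements, and must also absorb patients with no calorimetry, who are ineligible. It shows that incomplete measurement is expected, not how much.

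**2. Measurements due.** Count the first on day 3 and repeat every g days: number due = floor((stay - 3)/g) + 1.

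| Stay (days) | g = 3 | g = 4 |
|---|---|---|
| 11 | 3 | 3 |
| 14 | 4 | 3 |
| 21 | 7 | 5 |
| 28 | 9 | 7 |

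Take a 21-day patient measured once, on day 2. This patient is eligible and in the primary population. At record level, 0 of 1 REE values are missing (0%). Against the schedule, 4 of 5 (80%) to 6 of 7 (86%) are missing. The data are identical; only the denominator differs.

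**3. What the mixed model absorbs.** This was simulated, and every input is an assumption: 200 patients; stay 11 days plus an exponential time with mean 9; a slot every 3.5 days from day 2; REE about 20 kcal/kg with true slope 0.10 kcal/kg/day; patient SD 3, same-day state SD 1.5, residual SD 1.5; base skip probability 30%. A linear model with a random patient intercept was fitted to measured slots only, with 60 replicates per row. The log-odds of skipping rose, by the amount shown times day/10, either per SD of the last recorded REE or per SD of the patient's own level combined with the unrecorded same-day state.

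| Skipping driven by | Log-odds per SD | Slots skipped | REE blank in records | Mean slope | Bias | Average SE |
|---|---|---|---|---|---|---|
| Chance | 0 | 30% | 0% | 0.102 | 0.002 | 0.010 |
| Last recorded REE | 0.5 | 35% | 0% | 0.102 | 0.002 | 0.012 |
| Last recorded REE | 1.0 | 40% | 0% | 0.101 | 0.001 | 0.013 |
| Level and same-day state | 0.25 | 31% | 0% | 0.093 | -0.007 | 0.010 |
| Level and same-day state | 0.5 | 31% | 0% | 0.085 | -0.015 | 0.010 |
| Level and same-day state | 1.0 | 34% | 0% | 0.073 | -0.027 | 0.010 |

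The Monte Carlo error of each mean slope is about 0.001.

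- Skipping that follows recorded REE does essentially no harm, even at 40% skipped.
- Skipping that follows unrecorded state biases the slope, at worst by 0.027/0.010 = 2.7 average standard errors.
- In the state-driven rows the share skipped (31-34%) is close to the chance row (30%). A completeness table shows how much was skipped but cannot show why, so a sensitivity analysis is needed as well.

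The sign follows from letting high-REE states be skipped; it reverses if low-REE states are skipped.

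**4. Is state-driven skipping plausible here?** The Appendix 1 leak advice ties measurement directly to condition on the day. Because time-varying covariates are reported only on calorimetry days, that condition is not held for the skipped day.

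**The case against.** - **The gaps can be recovered.** Admission, investigation and discharge dates are all collected, and a date grid would fit the SAP's promise to study frequencies and patterns at each time point. This stands. The defect is an unspecified denominator, not lost information. A reader might infer that the check is bound to report a complete outcome; the text permits either reading. VO2 and VCO2, which the SAP also treats as outcomes, are optional and may be visibly missing.
- **The analysis is not defenceless.** A reader might infer that skipped measurements go wholly uncorrected. The mixed model uses actual days and handles skipping explained by recorded values or modelled covariates (step 3). The SAP has a fallback if MAR fails, and the protocol's Statistics section does not restrict its drop-out weights to live discharge. All this stands. However, the fallback names no method and depends on a check that may miss the gaps, and both sets of weights concern drop-out, not gaps during the stay.
- **Appendix 1 is mostly advisory.** High FiO2 or PEEP prompts a look at the manual and does not exclude a measurement. Rest periods of one to three hours delay a measurement and need not cost a 3-4-day slot. This stands, which is why leaks are the example used here. A reader might also suppose that patients off the ventilator are measured less often and differ in REE; no section says so.
- **Simulations return their inputs.** This stands. They show a pattern and do not estimate bias in this study.

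**Conclusion.** The point holds for REE and RQ. Three facts rest on the text alone: a due but undone calorimetry creates no record, the SAP's check has no expected-measurement denominator, and no named method covers patients who are in ICU but unmeasured. The exposed part is skipping driven by unrecorded state on the skipped day.

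Whether that biases the primary result, in which direction and by how much, cannot be determined from the documents. The simulated range, from nil to -0.027 on a true slope of 0.10, depends on an assumed 30% base skip rate, assumed variances, an assumed direction, and a model without the SAP's covariates or possible random slopes. The 33% margin should not be read as a predicted share of missing measurements.

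This should be settled in the SAP before analysis. It does not invalidate the design or the choice of primary model.

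**What to change.** In the SAP's missing-data paragraph:

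1. **Define the denominator.** From the dates already collected, build windows that respect the phases in the protocol's Hypothesis (day 1-3, 4-10, over 10): for example days 1-3, 4-7, 8-10, 11-14, 15-18 and so on, so that none crosses day 10. Count a window spent in ICU without calorimetry as missing REE and RQ, and state the rule for a window cut short by discharge or death. Report the share measured by phase and site. A patient measured on days 3, 7 and 11 keeps a 4-day interval yet leaves days 8-10 empty, so also tabulate gaps longer than 4 days.
2. **Keep the mixed model as primary and prespecify two sensitivity analyses beside it.** The first weights for a window not measured while still in ICU, using admission data and the last recorded calorimetry-day values. The second is a delta or pattern-mixture analysis over a stated range in both directions, for skipping driven by unrecorded state.
3. **Limitation to best supportive care.** If its date can be obtained without extra site work, treat later windows as planned end of measurement. Otherwise state that they cannot be told apart from skipped ones. The SAP already describes what the Australian cohort lacks, which suggests that data collection was well advanced, so a new field might mean retrospective chart review. Items 1 and 2 do not depend on it.

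Cost: SAP text and some programming on dates already held. The weighted intervals will be wider and reported completeness will look less favourable. Weights based on last recorded values remove only part of any bias; the delta analysis shows sensitivity to the remainder and does not remove it.

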## Outcomes

Primary:

- Change in REE (kcal/kg adjusted body weight\*/24 hours) over time in patients who stay in ICU for  $>10$  days.

\*Adjusted body weight is calculated as Ideal Body Weight (length in cm - 100) +  $\frac{1}{3}^*$ (Admission Body Weight - Ideal Body Weight). If admission body weight is less than ideal body weight, this value is used instead of adjusted body weight.

Secondary:

- Change in RQ over time in patients who stay in ICU for  $>10$  days.

- Change in REE and RQ over time in patients who stay in ICU for ≤10 days.

Exploratory:

Correlations between metabolic rate and CRP, albumin, urea/creatinine ratio, degree of organ failures (SOFA), ICU mortality, age and gender will be analyzed for hypothesis-generating purposes.

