## Statistics

Descriptive data will be presented as mean  $\pm$  standard deviation or median (interquartile range) as appropriate. The primary and secondary outcome measures will be analysed using a generalized linear mixed-effects model. Exploratory outcomes will be analysed using generalized linear regression models. If values are found to be not missing at random, conditional logistic regression censoring will be used to calculate inverse probability weights for accounting for difference in drop-out probabilities. The predetermined level of statistical significance is set to  $\leq 0.05$ .

A detailed statistical analysis plan will be published before the database is locked and analysis begins.

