## Statistical analysis plan (updated 2025-04-08)

For descriptive statistics, continuous variables will be presented as means  $\pm$  standard deviations (SD) or median [interquartile range (IQR)], as appropriate. Distributions will be visually inspected using histograms and assessed for normality using quantile-quantile plots.

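### The regression named for the censoring weights does not give the probability a weight needs, and the protocol and SAP differ on when the weights apply

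*Combined protocol and SAP*

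**What the plan says.** The weights appear in two places.

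- **Protocol, Statistics:** "If values are found to be not missing at random, conditional logistic regression censoring will be used to calculate inverse probability weights". The same section then promises that "A detailed statistical analysis plan will be published before the database is locked and analysis begins".
- **SAP (updated 2025-04-08), paragraph on missing data:** "Conditional logistic regression will be used to calculate the inverse probability of censoring weights to control for selective drop-out in patients discharged alive". The sentence just before it reads "If missing at random cannot be assumed, alternative modelling approaches will be considered".

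Neither place names strata, a time interval, covariates for the weight model, a way to obtain a baseline probability, or any stabilisation or truncation. Missingness is to be examined through summary tables and plots.

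The main analysis is a mixed model with random intercepts for patient and site. The primary outcome is the change in REE over time in stays of more than 10 days. Shorter stays are a separate secondary outcome: "Change in REE and RQ over time in patients who stay in ICU for ≤10 days".

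**The concern.** Follow-up ends at ICU discharge or death, so late REE values come only from patients who are still in the ICU. If those discharged alive differ in metabolic rate from those who remain, the late trajectory mixes real change with selection. The weights are the one device the plan aims specifically at live discharge.

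The named method stops short of producing them, because it is built to eliminate the quantity that a weight needs. The protocol's condition for using them is also one that data cannot satisfy. Left as it is, the text has the analyst settle the weight model, and whether the weights apply at all, after seeing the data.

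**Working it through.** The plan states no figure on this point, so there is none to reproduce. All rates, odds ratios and means below are assumed, because the documents give none.

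**1. What a weight needs.** With p_k the probability of live discharge in interval k among patients still in the ICU, the weight is w = Π 1/(1 − p_k). Each p_k must be an absolute probability.

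**2. What conditional logistic regression supplies.** Take a stratum of 10 patients, five at covariate level A and five at B, with odds ratio 2 and odds of leaving o at level A. Given that exactly one leaves, the probability that it is one particular B patient is 2o / (5o + 5·2o) = 2/15 = 0.133. The baseline o cancels.

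A second case has five patients, three at B and two at A, of whom two leave, both at B. The conditional likelihood is 4/(1 + 12 + 12) = 0.16, log −1.832581. Evaluated at intercepts −3, −1, 0 and 2, it was the same each time.

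Fitted to simulated data (60 strata of 100 patients, true odds ratio 2), the conditional model returned one parameter, the log odds ratio. An ordinary logistic model also recovered the baseline:

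| True baseline | Conditional model: odds ratio | Ordinary model: baseline |
|---|---|---|
| 0.05 | 2.18 | 0.050 |
| 0.15 | 2.05 | 0.147 |
| 0.30 | 1.85 | 0.304 |

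**3. Does the missing baseline cancel as a constant?** With odds ratio 2 and baseline p, the B-to-A ratio of weights per interval is 1 + p. Over three intervals:

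| Baseline p | Weight A, (1 − p)^−3 | Weight B | Ratio, (1 + p)^3 |
|---|---|---|---|
| 0.05 | 1.17 | 1.35 | 1.16 |
| 0.15 | 1.63 | 2.48 | 1.52 |
| 0.30 | 2.92 | 6.41 | 2.20 |

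The same odds ratio goes with different weights and different ratios of weights, so the baseline has to be estimated.

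**4. The protocol's trigger.** Suppose 60% of values are observed, with mean 22. If the missing 40% have mean 20, 22 or 24, the full mean is:

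- 0.6·22 + 0.4·20 = 21.2
- 0.6·22 + 0.4·22 = 22.0
- 0.6·22 + 0.4·24 = 22.8

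The observed data are identical in all three cases, so tables and plots of them cannot show that values are not missing at random. If drop-out does depend on unobserved values, weights built from recorded covariates correct the bias only in part.

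**5. The two texts side by side.** The protocol's weighting rule opens with an if. The SAP's weighting sentence has none; the condition stands in the sentence before it and leads to unspecified alternative models. On the plain reading the SAP weights unconditionally and the protocol does not. The protocol announces a SAP but does not say that it replaces this rule.

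**6. Where it matters for the primary outcome.** The Hypothesis section sets the phases at days 1-3, 4-10 and after day 10. In stays of more than 10 days nobody is discharged before day 10, so p_k = 0 and each factor is 1/(1 − 0) = 1 up to then. Live-discharge censoring arises only in the late phase.

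**The case against.** The strongest reply is that this is a slip of wording. The authors may mean ordinary logistic regression conditional on still being in the ICU, which does give usable probabilities. Even read literally, the baseline can be recovered from the exit counts. In the stratum of 10 with one exit, solving 5p_A + 5p_B = 1 with odds ratio 2 gives p_A of about 7%. This stands to a degree: the gap is cheap to close, and the weighted analysis is not impossible. But the documents name a different method in both places and describe no such step, so the text still needs correcting.

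Four stronger readings are tempting and are not supported:

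- **That the tabulated weights, such as 6.41, estimate the effect here.** They rest on assumed rates, and the analyst will hold exit counts that narrow the baseline. They show only that the baseline does not cancel.
- **That the whole primary REE trajectory is exposed.** The early and intermediate phases have no live-discharge drop-out in stays of more than 10 days. A correctly specified mixed model also accommodates drop-out that depends on observed REE.
- **That the SAP itself relies on an untestable trigger.** That requires carrying a condition across a full stop. The trigger is in the protocol.
- **That missed measurements in patients still in the ICU are left without provision.** The SAP's missing-data rules (for example "If missing at random can be assumed and frequencies are below 3% at each time point, this missingness will be ignored, and observations dropped") and the mixed model cover them. Limiting the weights to live discharge is not a defect.

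**Conclusion.** The concern holds in a limited form. The method named in both documents does not by itself yield censoring weights, and no stratum or baseline step is stated. This is a wrongly named method, not only missing detail. The protocol's trigger cannot be established from observed data, and the SAP does not repeat it, so the two texts need reconciling.

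The identification point follows from the form of the conditional likelihood and does not depend on the assumed rates. The size of any effect on REE cannot be computed from the documents. For the primary outcome it is confined to the late phase and reduced by whatever protection the mixed model gives under missing at random. The text should be corrected before the analysis, but the point does not invalidate the main model.

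**What to change.** In both the protocol's Statistics section and the SAP's missing-data paragraph:

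1. Replace conditional logistic regression with an ordinary (unconditional) pooled discrete-time logistic model of live discharge among patients still in the ICU. Condition on interval, last observed REE and recorded covariates available at all sites. SOFA is then left out, since the SAP makes an exception for it elsewhere: "except for the SOFA score, which is not available in the Australian subpopulation".
2. For the primary outcome, fit the model in stays of more than 10 days, with risk intervals starting at day 10. Earlier intervals contain no exits.
3. Carry the last recorded covariates forward when a measurement is missed, because they are collected only on calorimetry days.
4. State how death is handled, for example as a separate end of follow-up that is not weighted.
5. Use stabilised weights with a stated truncation rule.
6. Delete the protocol's trigger, state that the weights assume drop-out at random given those covariates, and say that the SAP governs.
7. Report the weighted result beside the unweighted mixed model. A delta-shift sensitivity analysis for departures from missing at random is optional.

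No new data are needed: calorimetry dates and covariates, discharge date and survival status are already collected. The cost is some redrafting, modest extra analysis and wider intervals for the weighted result.
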